#### 2625 **10.5.2.2 Secondary Efficacy Outcomes**

2626 The following CGM outcomes will be analyzed for the 24-hour period, daytime (6am-12mn) and  
2627 overnight (12mn-6am):

2628

2629 Hypoglycemia

2630 time <60 and <70 mg/dl

2631 • low blood glucose index (LBGI)

2632 • hypoglycemic events per 24 hours - defined as  $\geq 15$  consecutive minutes with a sensor glucose  
2633 <50 mg/dl

2634

2635 Overall Control

2636 • time in the target ranges of 70-180 and 70-120 mg/dl

2637 • glucose variability measured with coefficient of variation (CV) and with mean of daily difference  
2638 (MODD)

2639

2640 Hyperglycemia

2641 • Time >180 and >250 mg/dl

2642 • High blood glucose index (HBGI)

2643 • hyperglycemic events per 24 hours - defined as  $\geq 90$  consecutive minutes with a sensor glucose  
2644 >300 mg/dL

2645

2646 For all secondary analyses (including subgroup analyses), the false discovery rate (FDR) will be  
2647 controlled using the adaptive Benjamini-Hochberg procedure.

2648

#### 2649 **10.5.2.3 Other Secondary Outcomes**

2650 The following additional outcomes will be included in secondary analyses:

2651 • Total daily dose of insulin

2652 • Sensor accuracy:

- 2653                   ○ The following will be calculated using the Ascensia Contour Next One point-of care  
2654 glucose meter:  
2655                   ▪ MARD for the Dexcom G5 and Senseonics Eversense overall and in the following  
2656 SMBG ranges: < 70, 70–180, > 180, > 250
- 2657 • Daily at-home questionnaire:
    - 2658 ○ symptomatic hypoglycemia
    - 2659 ○ hypoglycemia requiring carbohydrate intervention
    - 2660 ○ alcohol use
    - 2661 ○ exercise
    - 2662 ○ nausea and/or vomiting
    - 2663 ○ use of a personal CGM as a part of usual care
  - 2664 • All glycemic CGM outcomes will be calculated for the first 24 hour period separately as a  
2665 secondary analysis of the BP as participants transition off of an MDI regimen onto closed loop  
2666 control.

#### 2667 **10.5.2.4 Safety Outcomes**

2668 All adverse events will be tabulated. Additionally, the following outcomes will be tabulated by treatment  
2669 period:

- 2670 • Episodes of severe hypoglycemia per participant
- 2671 • Episodes of diabetic ketoacidosis (DKA) per participant
- 2672 • Other serious adverse events per participant

2673 Due to the relatively short follow-up duration for this study, it is unlikely there will be enough such events  
2674 for a formal statistical comparison. However, if there are enough events, a Poisson regression that  
2675 accounts for correlated data from the same subject will be used to compare the number of events  
2676 between the three treatment periods. The amount of follow up will be included as an offset covariate to  
2677 compare the rates. Influence diagnostics will be reviewed and if outliers are present then the model will  
2678 be run without them and the results compared.

#### 2681 **10.5.2.5 Questionnaires**

2682 For each questionnaire completed at screening and the end of each one of the three 7-day treatment  
2683 periods, mean (SD) values or median (IQR) appropriate to the distribution will be given for the total  
2684 score and where indicated for each subscale.

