## 570 **CHAPTER 2: SYNOPSIS OF INSULIN-ONLY BP BRIDGING STUDY**

### 571 572 **2.1. Study Objectives**

- 573 • To serve as a transitional study, bridging to larger and longer outpatient pivotal studies  
574 using the insulin-only configuration of the bionic pancreas
- 575 • To assess the efficacy, safety, and reliability of the insulin-only configuration of the bionic  
576 pancreas in regulating glycemia using Humalog, or Novolog, in adult and pediatric  
577 participants and using Fiasp in adult participants in a short-term, outpatient study under  
578 real-world conditions;
- 579 • To assess safety of the insulin-only configuration of the bionic pancreas using Humalog,  
580 Novolog, and Fiasp (adults only), particularly with respect to severe hyperglycemia and  
581 hypoglycemia;
- 582 • To assess the impact of the insulin-only configuration of the bionic pancreas on quality of  
583 life and treatment satisfaction among study participants, their caregivers and/or family  
584 members;
- 585 • To document the interaction of the participants with the insulin-only configuration of the  
586 bionic pancreas device for human factors analysis, with the goals of identifying any  
587 problems with the user interface or instruction manual for the device that could lead to  
588 unsafe use of the device or an adverse event.
- 589 • To assess the efficacy, safety, and reliability of the insulin-only configuration of the bionic  
590 pancreas in the transition from autonomous glycemic control to either multiple daily  
591 injection therapy or insulin pump therapy.
- 592 • To assess the efficacy, safety, and reliability of the insulin-only configuration of the bionic  
593 pancreas using the Senseonics Eversense CGM as the input CGM in adult participants in  
594 a short-term outpatient study under real-world conditions.

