 925 3 –At Stanford during the RCT Period, a new Dexcom CGM sensor will be inserted at each day 0.  
 926 4 – At MGH during the RCT Period, Senseonics Eversense CGM sensor will be inserted during the period between  
 927 Screening and Day 0, at least 24 hours before Day 0.  
 928 5 – At MGH during the RCT Period, Senseonics Eversense CGM sensor will be removed at the Final Shutdown visit,  
 929 after the Post-Study Transition Period, or a later date, up to 90 days after insertion  
 930 6 – Questionnaires (see Chapter 7)  
 931 • Baseline questionnaires include: Diabetes Treatment Satisfaction Questionnaire - Status (DTSQs), Diabetes  
 932 Distress Scale (DDS), Hypoglycemia Fear Survey (HFS), Hypoglycemia Confidence, INSPIRE Survey. These  
 933 will be completed by the participant on the first Startup visit only.  
 934 • Day 7 of each experimental period: Diabetes Treatment Satisfaction Questionnaire - Change (DTSQc),

935  
936  
937  
938  
939  
940  
941  
942

Diabetes Distress Scale (DDS), Hypoglycemia Fear Survey (HFS), Hypoglycemia Confidence, INSPIRE survey, Bionic Pancreas User Opinion Survey (BPUOS) – BP period only  
7-- Study physicians will follow up with subjects and query about any adverse events within 48 hours following Senseonics Eversense insertion and removal.

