### 7.2. Brief Description of Questionnaires

#### 7.2.1. Diabetes Treatment Satisfaction Questionnaire - Status (DTSQs)

The DTSQs measures patient satisfaction with diabetes treatment. It consists of a 6 item scale for assessing treatment satisfaction and two additional items assessing perceived frequency of hyperglycemia and hypoglycemia. The DTSQs is meant for adults and older children. [name] has produced a version that is appropriate for BP studies for our use, along with a version for younger children. It is administered at the Initial Startup Visit. The DTSQs is valid and reliable. Administration time is less than 5 minutes.

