#### 7.2.2. Diabetes Treatment Satisfaction Questionnaire – Change (DTSQc)

Although the DTSQ is responsive to treatment changes, ceiling effects are often seen with this instrument, where maximum or close-to-maximum scores at baseline provide little opportunity for registering improvement. The DTSQc contains the same items as the DTSQs version but asks patients to consider their satisfaction with their current treatment compared with their previous treatment. The DTSQc is meant for adults and older children. [name] has produced a version that is appropriate for BP studies for our use, along with a version for younger children. It is administered at each Shutdown Visit. The DTSQc is valid and reliable. Administration time is less than 5 minutes.

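### As documented, the within-participant comparison of treatment satisfaction between bionic pancreas and usual care is not reliably interpretable, and section 10.5.2.5 does not specify one

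*Combined protocol and SAP*

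**What the plan says.** All references are to the Combined protocol and SAP.

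- **Objective (2.1).** One objective begins "To assess the impact of the insulin-only configuration of the bionic pancreas on quality of" life, and goes on to name treatment satisfaction.
- **Status form.** Section 7.2.1 says of the DTSQs: "It is administered at the Initial Startup Visit. The DTSQs is valid and reliable". Footnote 6 of the adult schedule (2.3) says that the baseline set, which includes the DTSQs, "will be completed by the participant on the first Startup visit only". The pediatric RCT schedule (2.5) says the same.
- **Change form.** Section 7.2.2 says of the DTSQc: "It is administered at each Shutdown Visit. The DTSQc is valid and reliable". The adult schedule agrees: "Day 7 of each experimental period: Diabetes Treatment Satisfaction Questionnaire - Change (DTSQc", with no DTSQs in that list. The form asks patients "to consider their satisfaction with their current treatment compared with their previous" treatment. No section says which treatment that is.
- **Analysis (10.5.2.5).** The rule starts "For each questionnaire completed at screening and the end of each one of the three 7-day treatment" period and provides a mean (SD) or median (IQR) for total scores and, where indicated, subscales. Section 10.6.2 carries this over to the Pediatric RCT Period.

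**The concern.** A crossover is well suited to asking whether the same person is more satisfied on the BP than on usual care. That needs either a status score after each period or a change score with one fixed reference. The plan collects no status score after any period, and its change score has a reference that can move with the randomised order.

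A mean DTSQc for the UC period could then pool people comparing UC with pre-study care, with washout care, or with a BP period that they have just finished. Such a mean would depend partly on period order. The satisfaction part of the objective would then rest on per-period averages whose meaning is not fixed, with no planned paired difference.

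**Working it through.** The plan states no sample size, power or effect size for the questionnaires, so there is no figure to reproduce. The check has three parts.

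**1. When each form is completed (2.3, 2.5, 7.2)**

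| Form | First Startup | After BP | After UC |
|---|---|---|---|
| DTSQs | yes | no | no |
| DTSQc | no | yes | yes |
| DDS, PAID (children), HFS, HCS, INSPIRE | yes | yes | yes |
| BPUOS | no | yes | no |

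Participants with a DTSQs score after any RCT period: 0 of 36 + 20 = 56. The scales in the third row are described in 7.2 as measuring distress, fear, confidence or experience with automated insulin delivery. None is described there as a treatment-satisfaction scale. Read literally, the rule in 10.5.2.5 needs a form completed at baseline and at each period end, and neither DTSQ form meets that. The rule also says screening, where 7.2.1 says "It is administered at the Initial Startup Visit".

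**2. What the DTSQc reference could be**

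Inputs: 36 adults in three periods and 20 children in two, in random order (2.2); washouts of 5 to 9 days (4.1); usual management resumed on coming off the BP (5.9). Section 4.3 says only that the randomization list uses a block design, so balanced orders are an assumption. Let A be BP with usual analog, F be BP with Fiasp, and U be usual care.

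| Adult order | U follows a BP period | Second BP period directly follows the first |
|---|---|---|
| A-F-U | yes | yes |
| F-A-U | yes | yes |
| A-U-F | yes | no |
| F-U-A | yes | no |
| U-A-F | no | yes |
| U-F-A | no | yes |

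- Ambiguous at the UC shutdown, adults: 36 × 4/6 = 24.
- Ambiguous at the UC shutdown, children (BP first in 1 of 2 orders): 20 × 1/2 = 10.
- Ambiguous at the second BP shutdown, adults: 36 × 4/6 = 24. In the other 36 × 2/6 = 12, a UC period lies in between.

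Here ambiguous means that the previous treatment could be the earlier BP period, washout usual care or pre-study care. The adult counts are the same if only three orders forming a Latin square are used (for example A-F-U, F-U-A, U-A-F: 36 × 2/3 = 24 for each). Otherwise, each adult moved between a UC-first order and another order changes the UC-shutdown count by one. The 0 of 56 does not depend on balance.

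**3. Where the reference is effectively fixed**

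In period 1 the only earlier treatment is pre-study care. That gives 36 × 4/6 = 24 adults on BP against 36 × 2/6 = 12 on UC, and 10 children against 10. It is a comparison between groups, not within participants.

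**The case against.** The strongest reply is that the reference is stable in practice. Washouts separate the periods, and participants resume usual management when they leave the BP (5.9). Taken literally, the treatment immediately before every period is therefore usual care. In addition, 7.2.2 says that a BP-study version of the form was produced, and 7.1 leaves administration to a procedures manual. Either may name the reference. This stands as a possibility. It does not remove the need to state the reference, because a participant asked after UC may well think of the BP period before the washout.

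Three stronger readings are tempting, and the document does not support them.

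- **That the trial cannot show a satisfaction difference, or has no common scale.** The same person completes the DTSQc after both BP and UC. With a fixed reference, the paired contrast is interpretable, and period 1 already allows a smaller between-group comparison.
- **That usual care in period 1 is simply rated against itself.** The UC period adds study CGM supplies (5.3) and round-the-clock remote monitoring (5.5), so the rating is a useful control. For the same reason, the baseline DTSQs is not a clean substitute for a UC score.
- **That every adult has an ambiguous reference at the second BP shutdown.** In the two orders with UC in the middle, the preceding period is usual care.

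On analysis, 10.5.2.5 can be read as listing occasions rather than requiring both, in which case both DTSQ forms are summarised. Section 10.5.2.1 says that models for exploratory outcomes parallel the primary ones, and Chapter 10 promises a detailed SAP. But 10.5.2.5 names no contrast, whereas 10.5.2.4 does name a model for safety events. A model would not repair an undefined reference. Section 7.1 also says that questionnaires in general are completed at the Initial Startup and every Shutdown Visit, which conflicts with the specific schedules for both DTSQ forms.

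The choice of the DTSQc is reasoned: 7.2.2 cites ceiling effects with the DTSQ. That argues for keeping the DTSQc at every Shutdown Visit, including UC. It does not argue against adding the DTSQs.

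**Conclusion.** The point holds in a limited form. As documented, the within-participant BP-versus-UC satisfaction contrast is not reliably interpretable, and 10.5.2.5 does not specify one. No participant has a post-period status score. Under balanced orders, the DTSQc reference is ambiguous for two thirds of adults (24 of 36) and half of children (10 of 20) at the UC shutdown, and for two thirds of adults at the second BP shutdown.

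This rests on balanced orders and on the documents available. If the adapted form or the manual fixes the reference, the ambiguity goes, but the missing status scores and the unspecified paired contrast remain. The questionnaires are exploratory in a feasibility study, and the primary glucose and safety outcomes are untouched. It is a worthwhile, inexpensive improvement, not a defect that undermines the trial.

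**What to change.** 1. In 2.3, 2.5, 2.6 and 7.2.1, give the DTSQs at every Shutdown Visit as well as at the first Startup Visit. Align 7.1 with the resulting schedule.
2. Keep the DTSQc at all Shutdown Visits, including UC, and state in 7.2.2 that the comparison is with usual treatment before the study. If the adapted form already says so, one sentence is enough.
3. In 10.5.2.5 (and so in 10.6.2), report the within-participant BP-minus-UC difference with a 95% confidence interval for the DTSQs, the DTSQc and the other repeated scales, separately for each BP period in adults. Word the rule so that both DTSQ forms are clearly covered.
4. In 10.5.2.5, replace screening with the Initial Startup Visit.

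Cost: one form already in use, stated in 7.2.1 to take under 5 minutes, at three Shutdown Visits per adult and two per child in the RCT Periods. The DTSQs may show a ceiling effect, which the retained DTSQc offsets. Sample size and treatment do not change.

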#### 2685 **10.5.3 Subgroup Analyses**

2686 Subgroup analyses/assessments of effect modification (interaction) will be conducted for each of the  
2687 two main outcomes (time <54 mg/dl and mean glucose). These analyses will include, but will not be  
2688 limited to, evaluating potential differences between sites, including differences between the RCT Period  
2689 at the MGH site using the Senseonics Eversense as the input to the iLet and the RCT Period at the  
2690 Stanford site using the Dexcom G5 CGM as the input to the iLet. The general approach for these  
2691 analyses will be to add an interaction term for the subgroup factor by treatment into the models used  
2692 for the primary analyses. Moreover, the continuous variables will be used in the models, while for  
2693 presentation purposes, a binary variable will be created.

2694 Summary statistics appropriate to the distribution will be tabulates in each subgroup by treatment period.  
2695 The study is not expected to have sufficient statistical power for definitive conclusions in subgroups and  
2696 statistical power will be low to formally assess for the presence of interaction. Interpretation of subgroup  
2697 analyses will depend on whether the overall analysis demonstrates a significant treatment group  
2698 difference. In the absence of such an overall difference and if performed, subgroup analyses will be  
2699 interpreted with caution and used to suggest hypotheses for further investigation in future studies.

2700 The following baseline factors will be assessed:

- 2705 • Age
- 2706 • Baseline HbA1c
- 2707 • Study center
- 2708 • Insulin method: pump versus injection (participants will be recruited with a 1:1 ratio)
- 2709 • T1D duration

2710

#### 2711 **10.5.4 Analyses for the Two BP Treatment Periods Only**

2712 The amount of time the system is active and CGM data available to the system, and the frequencies of  
2713 different system errors during the two BP treatment periods only will be reported.

2714

#### 2715 **10.5.5 Additional Tabulations and Plots**

2716 The following tabulations will be performed:

- 2717 - Baseline demographics and clinical characteristics
- 2718 - Flowchart accounting for all subjects and both phases
- 2719 - Visits and phone contacts as scheduled
- 2720 Number and reasons for unscheduled visits and phone contacts
- 2721 - Protocol deviations
- 2722 - Twenty-four hour plots with median line and IQR bands for % CGM <54 mg/dl, >180 mg/dl,  
2723 mean, 70-180 mg/dl, and coefficient of variation by the three periods.

2724

### 2725 **10.6. Pediatric RCT Period**

2726

#### 2727 **10.6.1. Summary**

2728 Twenty pediatric participants (age 6–17 years) will be enrolled at two sites and will be randomly  
2729 assigned to the following study periods: (1) the iLet in the insulin-only configuration (with the iLet pigtail  
2730 adapter and iLet ready-to-fill insulin cartridge, the Contact Detach infusion set, and the Dexcom G5  
2731 CGM) using insulin analog that they use for their usual care (either Humalog or Novolog)and (2) UC  
2732 (with Dexcom G5 CGM).

2733

#### 2734 **10.6.2. Outcomes**

2735 All the above Adult RCT Period outcomes and analyses will be replicated here with the exceptions that,  
2736 since there are only 2 treatment periods here (instead of 3 above). For the primary outcomes, a similar  
2737 hierarchical gatekeeping procedure as the one described above for Adult RCT Period will be used; the  
2738 list will include only two outcomes in this order:

- 2739 1. Mean glucose for (1) BP with analog insulin vs. (2) UC
- 2740 2. Time <54 mg/dl for (1) BP with analog insulin vs. (2) UC

2741

### 2742 **10.7. Post-Study Transition to Usual Diabetes Management**

2743

#### 2744 **10.7.1. Summary**

2745 All adult and pediatric participants randomized to complete a BP period as their final study period in  
2746 the RCT period will participate in this post-study transition period. For 48 hours immediately after the  
2747 RCT period, they will be discharged to their usual care using the iLet's dosing recommendations.  
2748 They will be monitored remotely and continue to follow all study procedures.

2749

#### 2750 **10.7.2. Outcomes**

2751 No formal statistical comparisons will be done for the Post-Study Transition Period.

2752 Since the main aim of the Post-Study Transition Period is to verify safety and feasibility, plus some  
2753 trends in efficacy; the following outcomes will be considered:

- 2754 • Safety:
  - 2755 ○ Episodes of severe hypoglycemia as defined in section 8.1.2.1
  - 2756 ○ Episodes of diabetic ketoacidosis (DKA) as defined in section 8.1.2.2

- 2757           ○ Other serious adverse events
- 2758       • Hypoglycemia: time < 54 mg/dl
- 2759       • Mean CGM glucose
- 2760       • Daily at-home questionnaire:
  - 2761           ○ symptomatic hypoglycemia
  - 2762           ○ hypoglycemia requiring carbohydrate intervention
  - 2763           ○ alcohol use
  - 2764           ○ exercise
  - 2765           ○ nausea and/or vomiting
- 2766
- 2767
- 2768
- 2769

## CHAPTER 11: DATA COLLECTION AND MONITORING

2770  
2771  
2772  
2773  
2774  
2775  
2776  
2777  
2778  
2779  
2780  
2781  
2782  
2783  
2784  
2785  
2786  
2787  
2788  
2789  
2790  
2791  
2792  
2793  
2794  
2795  
2796  
2797  
2798  
2799  
2800  
2801  
2802  
2803  
2804  
2805

### 11.1. Case Report Forms and Device Data

The main study data are collected through a combination of electronic case report forms (CRFs) and electronic device datafiles obtained from the study software and individual hardware components (BP, CGM, SMBG meter, and blood ketone meter). These electronic device files and electronic CRFs from the study website are considered the primary source documentation.

### 11.2. Quality Assurance and Monitoring

Designated personnel from the Coordinating Center will be responsible for maintaining quality assurance (QA) and quality control (QC) systems to ensure that the clinical portion of the trial is conducted and data are generated, documented and reported in compliance with the protocol, GCP and the applicable regulatory requirements. Adverse events will be prioritized for monitoring.

A risk-based monitoring (RBM) plan will be developed and revised as needed during the course of the study. The data of most importance for monitoring at the site are participant eligibility and adverse events. Therefore, the RBM plan will focus on these areas. As much as possible, remote monitoring will be performed in real-time with on-site monitoring performed to evaluate the verity and completeness of the key site data. Elements of the RBM may include:

- Qualification assessment, training, and certification for sites and site personnel
- Oversight of Institutional Review Board (IRB) coverage and informed consent procedures
- Central (remote) data monitoring: validation of data entry, data edits/audit trail, protocol review of entered data and edits, statistical monitoring, study closeout
- On-site monitoring (site visits): source data verification, site visit report
- Device accountability
- Communications with site staff
- Patient retention and visit completion
- Quality control reports
- Management of noncompliance
- Documenting monitoring activities
- Adverse event reporting and monitoring

JCHR representatives or their designees may visit the study facilities at any time in order to maintain current and personal knowledge of the study through review of the records, comparison with source documents, observation and discussion of the conduct and progress of the study.
